**Table 6. Bedside actions based on patient oxygen saturations**

Patient Oxygen Saturation	Action
Any time oxygen saturation falls below SpO2 target range	
 
Assess infant for problems and reposition as needed
 
Troubleshoot bCPAP system (check connections, nasal interface, assess for presence of secretions)
 
Check pulse oximeter sensor and reposition or replace as needed
 

Oxygen saturation is still below SpO2 target range (but still at or above 80%) for 5 minutes or Oxygen saturation falls below 80% for 1 minute	
 
Increase percentage of oxygen delivered
 
Monitor saturations closely for 10-15 minutes after making the change
 

Oxygen saturation drops severely and the baby needs emergency attention	
 
Increase oxygen percent immediately
 

Oxygen saturation above SpO2 target range for 5 minutes	
 
Decrease percentage of oxygen delivered
 
Monitor saturations closely for 10-15 minutes after making the change
 

There are times when the air compressors on the unit may not be functioning or are unavailable due to high demand. This creates two possible scenarios for oxygen blending during the study (Figure 6, Tables 7 and 8).

**Figure 10. Scenarios of oxygen blending for enrolled patients during study.** Patient's blending scenario may change throughout course due to changing availability/functioning of air compressors.

**Table 7. Scenario 1- Adjusting oxygen delivery in current standard of care (when air compressor is available):**

Percent Oxygen Required	How to Deliver
Lowest possible	All flow from air compressor No flow from the oxygen concentrator
Low	Minimal flow from oxygen concentrator, most from air compressor
Middle	Flow split between air compressor and oxygen concentrator
High	Most flow from oxygen concentrator, minimal from air compressor
Highest possible	All flow from oxygen concentrator No flow from the air compressor

**Table 8. Scenario 2- Adjusting oxygen delivery with PATH blender (when no air compressor is available):**

Percent Oxygen Required	How to Deliver
Low	Place 37% blender ^ in line
Higher	Place 60% blender ^ in line
Highest possible	All flow from oxygen concentrator No blender use

^ *The actual percentage of oxygen delivered to patient will be dependent on the concentration of oxygen provided by concentrator.*

All patients, whether enrolled in the study or not, will receive standard care after bCPAP treatment. There will not be any study-related treatment or follow up provided at the end of this study. Patients discharged from the newborn care unit are offered follow-up visits free of cost at Kiwoko Hospital as is the standard of care.

### **Study Costs**

All neonates who are admitted to the NICU and require bCPAP therapy can access it regardless of the parent’s financial means. The hospital charges a base rate for admission, which is not affected by length of stay, nor basic treatments provided - bCPAP therapy is considered a part of basic treatment and is not an extra charge. At the time of discharge, patients are required to pay their bill. Families without financial means to pay their bill at discharge are considered for financial aid from the hospital.

## **5.6 Study variables**

See Table 10 in Section 5.8.2

## 5.7 Data collection

### Healthcare workers:

From the onset of the study, consented healthcare workers will be observed as they set up and use the PATH bCPAP kit with or without the oxygen blenders. If they have consented, healthcare workers may also be photographed, video or audio recorded. Observations conducted across the study period will ensure that different levels of familiarity with use of the blenders are observed.

- Right after the observation (or the next day if not enough time available), the healthcare workers will be asked to complete a usability scale related to their experience with the PATH bCPAP kit with or without oxygen blenders. We will collect data from healthcare workers in all 15 cases of use of the PATH bCPAP kit with the blenders.
- Up to 15 of those same healthcare workers who were observed using the PATH bCPAP kit with the blenders will also be interviewed within the first five days of having used the PATH bCPAP kit and blenders for the first time.
- Additionally, five of those healthcare workers that used the PATH bCPAP kit with blenders three or more times during study period will be interviewed again toward the end of the study, to probe if their experience changed with familiarity of use.

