**Inclusion criteria:**

- Healthcare workers (nurses and midwives) who care for patients on bCPAP therapy with or without blenders at Kiwoko’s newborn unit during the period of study, and who provided informed consent to be observed and interviewed

**Exclusion criteria:** Healthcare workers that did not provide informed consent to be observed or interviewed.

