### 5.7.1 Training

In order to standardize care, nurses and physicians working in the newborn care unit will receive mandatory refresher training two weeks prior to start of data collection. Refresher training will include clinical presentation of respiratory failure and providing treatment with

bCPAP. They will also receive training in the use of the PATH bCPAP kit, including the blenders. Healthcare workers who complete training will be recorded in a list and these are the only providers who will care for PATH bCPAP patients during the period of study. It is assumed the PATH bCPAP kit with oxygen blenders will be no more time intensive than the current system to set up or use, and there will be no additional charting requirements for the nurses.

To avoid disrupting clinical care of patients and to increase data quality, research assistants will be present 24 hours a day, all days of the week, at the bedside of patients receiving bCPAP therapy with or without PATH blenders during the study period. Research assistants will be nursing students trained to record clinical data points of patients on bCPAP therapy. They will serve in a purely observational role and will not provide patient care, nor make any modifications to treatment.

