#### Healthcare worker consent:

Healthcare workers (nurses and midwives) who care for patients receiving bCPAP therapy with or without blending in the Kiwoko unit will be approached to participate in the study by research personnel who are not in a supervisory position to the worker.

Risks as well as benefits and alternatives to study participation will be discussed. Consent forms will include a contact of the Makerere IRB chairperson. Consent will be documented with signature. Consent will be obtained for obtaining photographs, video or audio recording of the healthcare worker or they may decline this.

Healthcare personnel will have access to the country principal investigator (PI) to ask further questions. The health care worker can withdraw from the study at any time during or after the study is complete.

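### Worker data in all 15 blender cases are promised but not guaranteed: the data depend on worker consent, care depends only on training, and the forms are not triggered at first blender use

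*Combined protocol and SAP*

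**What the plan says.** Section 5.7 (Data collection, Healthcare workers) makes the commitment: "We will collect data from healthcare workers in all 15 cases of use of the PATH bCPAP kit with the blenders". The same section limits who is watched: "consented healthcare workers will be observed as they set up and use the PATH bCPAP kit with or without the oxygen blenders". The usability scale is completed straight after the observation or on the following day, so it too is reached through consent.

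Section 5.7.1 (Training) sets the condition for giving care: "Healthcare workers who complete training will be recorded in a list and these are the only providers who will care for PATH bCPAP patients". Consent to the research is not mentioned there.

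Section 5.4 (Study population, Healthcare workers) includes "Healthcare workers (nurses and midwives) who care for patients on bCPAP therapy with or without blenders", provided they agreed to both observation and interview. The exclusion line joins the two with a different conjunction: "Healthcare workers that did not provide informed consent to be observed or interviewed". Section 5.9.1 (Healthcare worker consent) allows a worker to withdraw at any point, and already treats photographs and recordings as something a worker may decline separately.

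Section 5.3 (Sample size) expects all or most of 40 permanent workers to be observed, subject to consent, and up to 15 to be interviewed. It stops enrolment once 15 infants have been treated with a PATH blender.

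In section 5.7.2, Table 10 marks the set-up observation form at bCPAP initiation only, and Table 12 marks the usability form at each PATH bCPAP initiation. The Table 10 column for starting or changing a blender triggers Patient Data Form 2 alone.

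**The concern.** Two different conditions govern one set of cases. Training decides who may handle a PATH infant, and consent decides whether that handling yields worker data. No section links them. A blender case handled only by a worker who has not consented, or who has withdrawn, would count towards the 15 and close enrolment, yet provide no observation or usability form. The plan has no rule for replacing such a case or reporting it.

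The inclusion wording may lose workers needlessly. Read literally, someone willing to be watched and to complete the scale, but not to be interviewed, is ineligible, although most workers will never be interviewed.

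There is also a gap in timing. Section 5.5 expects some infants to receive both blending methods as compressors fail or become free. A blender first placed during the course of treatment triggers neither worker form under Tables 10 and 12, even if every worker consents.

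Both primary objectives are affected. Set-up time, correct set-up and user errors contribute to the operational feasibility index (section 5.8.2), and the usability total comes solely from the worker form (Table 13). With 15 cases, each one lost is 1/15 = 6.7% of the blender experience.

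**Working it through.** **The plan's own figure.** Table 3 gives 15 blender infants at 3 months. Its inputs are 37 bCPAP patients, 80% parental consent and a compressor unavailable about 50% of the time: 37 × 0.80 × 0.50 = 14.8, which rounds to 15. The target reproduces. It counts infants only; worker consent does not enter the calculation.

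**Inputs for coverage.** The number of cases is n = 15 (section 5.3). The share of workers who consent, c, is not given beyond all or most of 40, so I take 95%, 90% and 80%. Out of 40 workers these are 2, 4 and 8 non-consenters. The number of workers per case who could supply the data, m, is not given either; I take 1 and 2, with 4 as a further check. Workers are assumed to be spread evenly and independently over cases.

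**Formulas.** A case is covered with probability 1 − (1 − c)^m. The expected number of uncovered cases is 15 × (1 − c)^m. The chance that all 15 are covered is [1 − (1 − c)^m]^15.

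**One worker per case (m = 1):**

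| c | Expected covered | Expected lost | Chance of all 15 |
|---|---|---|---|
| 95% | 14.25 | 0.75 | 0.95^15 = 46% |
| 90% | 13.5 | 1.5 | 0.90^15 = 21% |
| 80% | 12.0 | 3.0 | 0.80^15 = 3.5% |

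An 80% chance of full coverage would need c = 0.80^(1/15) = 98.5%.

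**Either of two workers (m = 2):**

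| c | Case covered | Chance of all 15 |
|---|---|---|
| 95% | 1 − 0.05² = 0.9975 | 0.9975^15 = 96% |
| 90% | 1 − 0.10² = 0.99 | 0.99^15 = 86% |
| 80% | 1 − 0.20² = 0.96 | 0.96^15 = 54% |

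With any of four workers, even c = 80% gives (1 − 0.20⁴)^15 = 97.6%.

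**Which m fits.** Table 10 marks the set-up observation at initiation only, so workers on later shifts cannot supply that form. This favours a small m for set-up data, but the documents do not say how many workers set up each kit.

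**Timing gap.** These figures assume that a form is triggered in every blender case. Where the blender first goes in after initiation, Tables 10 and 12 schedule no worker form at that event, so the loss would come on top. The documents do not say how many of the 15 cases this would be.

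**The case against.** The strongest reply is that no shortfall has been shown. Section 5.3 expects nearly the whole unit to take part. Median bCPAP duration is 3 days on eight-hour shifts, so several workers may handle each infant, and section 5.7 does not say that only the worker who started the case counts. Even with one worker per case, the expected loss at 90% to 95% consent is about one case. In a descriptive study without a hypothesis-driven sample size, the chance of perfect coverage is a demanding yardstick. Operational feasibility also draws on Patient Data Form 2 and the concentrator form, and usability forms are due at every PATH initiation, up to 40 infants. The consent forms are in an appendix that is not available here and may already separate the items.

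Most of this stands. It limits the size of the problem, but it does not supply the missing link between consent and care or a form trigger at first blender use.

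Three stronger readings do not stand:

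- A reader might infer that coverage will fail. The documents show only that it is unsecured; care by non-consenting workers is inferred from silence, not stated.
- A reader might infer that cases are lost because physicians are trained ("nurses and physicians working in the newborn care unit will receive mandatory refresher training") while section 5.9.1 approaches only "Healthcare workers (nurses and midwives) who care for patients receiving bCPAP therapy". No section has a physician setting up a kit or placing a blender, and section 5.5 gives oxygen titration to nurses.
- A reader might infer that results will favour the more confident workers. Selection by willingness is plausible, but neither its direction nor its size can be derived from the documents.

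**Conclusion.** The promise of worker data in all 15 blender cases is not guaranteed. Data depend on consent, care depends on training, and enrolment stops on infants treated. On the literal inclusion wording, workers who decline only the interview are lost without need; the exclusion wording leaves this ambiguous.

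The size rests on two quantities that the documents do not give. Over consent shares of 95% to 80%, the chance of full coverage runs from 46% down to 3.5% with one worker per case, and from 96% down to 54% if either of two will do. The one-worker figures are the unfavourable end of the range, not a forecast. The trigger gap in Tables 10 and 12 is separate and would remain under full consent.

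The point merits a change because it touches both primary objectives and is cheap to put right. It does not show that the results will be biased, and it gives no ground for adding physicians to the worker population.

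**What to change.** 1. In sections 5.4 and 5.9.1, make observation plus the usability form one consent item and the interview an optional second item, as is already done for photographs and recordings. Align the inclusion and exclusion wording with this.
2. In section 5.7, replace the commitment to all 15 cases with one to all blender cases handled by a consenting worker. Report the number of blender cases with and without worker data beside each set-up and usability result.
3. In Tables 10 and 12, trigger the observation and usability forms at first blender use as well as at bCPAP initiation.

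Items 1 and 2 change only protocol and consent-form wording, at the price of a slightly less favourable stated coverage. Item 3 adds a few forms, which can be completed with the research assistants who are already at the bedside around the clock (section 5.7.1).

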### Data Collection:

A quality assurance activity will take place the week prior to the study to ensure HCW are following protocols re: oxygen blending with the existing Kiwoko bCPAP kit. No study data will be collected at this time.

**Table 9. Study Timeline**

Timeline	Activity
2 weeks before study start	Train In-Unit Research Assistants
2 weeks before study start	Train Data Team on REDCap Data Entry
2 weeks before study start	bCPAP and blending training for healthcare workers (education on PATH bCPAP kit and blender)
1 week before study start	Quality Assurance with Kiwoko bCPAP kit
Study start	Change to PATH bCPAP/blender and start data collection
Throughout data collection	Initial interviews with HCW after their initial use of PATH bCPAP kit/blender
3-4 months into data collection	Repeat interviews for selected healthcare workers with more familiarity of use of PATH bCPAP kit/blender
4 months total of data collection	Study end (3.5 months of PATH kit use)

### 5.7.1 Training

In order to standardize care, nurses and physicians working in the newborn care unit will receive mandatory refresher training two weeks prior to start of data collection. Refresher training will include clinical presentation of respiratory failure and providing treatment with

bCPAP. They will also receive training in the use of the PATH bCPAP kit, including the blenders. Healthcare workers who complete training will be recorded in a list and these are the only providers who will care for PATH bCPAP patients during the period of study. It is assumed the PATH bCPAP kit with oxygen blenders will be no more time intensive than the current system to set up or use, and there will be no additional charting requirements for the nurses.

To avoid disrupting clinical care of patients and to increase data quality, research assistants will be present 24 hours a day, all days of the week, at the bedside of patients receiving bCPAP therapy with or without PATH blenders during the study period. Research assistants will be nursing students trained to record clinical data points of patients on bCPAP therapy. They will serve in a purely observational role and will not provide patient care, nor make any modifications to treatment.

### 5.7.2 Tools

See “Data Collection Forms” in Appendix D, these include:

- Patient Data Form 1 (Demographics and Admission Clinical Data)
- Patient Data Form 2 (Clinical Course and bCPAP Settings)
- Concentrator FIO2 Output Form
- Newborn Unit Shift Form
- Adverse Event Record
- Unanticipated Adverse Device Effects (UADE) Event Record
- Healthcare Worker (HCW) Usability Form
- Healthcare Worker (HCW) Observation of bCPAP With or Without Blenders Set-up Form
- Healthcare Worker (HCW) Initial Interview Guide
- Healthcare Worker (HCW) Follow-Up Interview Guide

Data will be collected on the forms at the following timepoints:

Table 10. Patient Specific Data Collection Timing:

Form	Event					
	bCPAP initiation	Blender start or change	bCPAP pressure change	bCPAP stopped	Patient discharged/ deceased	Unanticipated Adverse Device Effect or Adverse Event
Healthcare Worker (HCW) Observation of bCPAP With or Without Blender Set-Up	X					
Patient Data Form 1 (Demographics)	X			X	X	

and Admission Clinical Data)						
Patient Data Form 2 (Clinical course and bCPAP settings)	X	X	X	X		
Adverse Event Record						X
Unanticipated Adverse Device Effects (UADE) Event Record						X

Table 11. Unit/Equipment Specific Data Collection Timing:

	Each Shift	Each Week
Newborn Unit Shift Form	X	
Concentrator FIO 2 Output Form		X

Table 12. Nursing Specific Data Collection Timing:

	With Each PATH bCPAP initiation	Initial Interview	Final Interview
HCW Initial Interview Guide		X	
HCW Follow-up Interview Guide			X
HCW Usability Form	X		

## 5.8 Data management and analysis

### 5.8.1 Data management

All quantitative data will be collected using case report forms and entered in REDCap software. The software will be programmed with internal checks to ensure completeness and logical entries. Data will be later transferred to Stata V.15 for analysis.

Qualitative data analysis: paper transcripts, files of data and audio recordings from in-depth interviews will be kept securely under key and lock. Audio recordings will be downloaded and stored in a password protected computer and transcribed. A codebook with code definitions and a data analysis plan will be developed before the coding exercise starts. As a quality control measure, about 10 primary documents will be double coded (manually and electronically). Transcripts will then be exported into NVivo software for electronic coding and analysis using content thematic approach guided.

### 5.8.2 Data analysis

Table 13 presents a summary of variables, data sources and analysis plan. We will evaluate operational feasibility by analysing the domains below; each domain uses information from mixed data sources. We will create an index measure for each domain, all of which will be weighted equally. We will sum these index measures to determine overall operational feasibility.

- Ease of correct use: Median set-up time, frequency of correct set up, time to change blender, types and frequencies of user errors, frequency of changes to blend provided per day, frequency of bCPAP level adjustment per day
- Integration into service delivery: Count of patients treated with PATH bCPAP, Frequency of blending via air compressor and PATH blenders, Frequency of known bCPAP complications
- Confirmation of device functionality: Median and IQR of: FIO2 administered by PATH blenders (determined by blender used and FIO2 provided by concentrator), level of bCPAP (and min/max), total air/oxygen flow to bCPAP device (subset)
- Concentrator output: Ability to determine FIO2 delivered to patient
- Device malfunction: Frequency of device malfunctions with and without adverse events

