#### Patients:

The sample size for patients will allow for reasonable frequency of use of the device by healthcare workers and at the same time for risk mitigation in line with an early feasibility study.

During the period of study, up to 40 patients will be treated with the PATH bCPAP. **This maximum of 40 patients in this study is selected to ensure that we will achieve our required sample size of 15 infants who are treated with the PATH bCPAP kit and blender.** All enrolled patients will receive treatment with the PATH bCPAP kit (cannula, tubing, bubbler bottle), although not all may require the use the PATH blender. Patients may have two methods of blending available during the study according to the following decision logic (Figures 8 and 9):

- **An air compressor will be used as first choice if available.** The number of patients in this scenario is dependent on the availability of functional air compressors; see Study Site section 5.2 for further details.

- When a functional air compressor is not available, the patient will receive treatment with the PATH blenders. Our aim is to treat 15 patients using the PATH blenders. No additional patients will be enrolled in the study after this target has been achieved.

[figure not shown]

Figure 8. Methods of oxygen blending during study. The study may enrol up to 40 patients on the PATH bCPAP kit to ensure a subset of 15 patients will also use the PATH oxygen blender (B).

[figure not shown]

Figure 9. Flowchart of expected patient recruitment (percentages and n's estimated). A total of 30+ enrolled patients treated with PATH bCPAP may be required to ensure the target of 15 patients are also treated with the PATH blenders.

Sample size for patients is being estimated knowing that at Kiwoko Hospital, an average of 12 patients are treated with bCPAP therapy per month[35], per the Table 3 below.

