**Table 3. Expected recruitment and PATH blender use based on study length and functional compressors.**

Study length (in months)	Expected number of patients on CPAP	Enrolled patients with 80% consent	Patients with use of PATH blender (air compressor not available ~50% of time)
1	12	9	4
2	24	19	10
3	37	29	15
4	49	39	20
5	61	48	24

Healthcare workers:

**Bedside observations:** We will observe the care of bCPAP patients with or without PATH blender use provided by healthcare workers in the newborn care unit. This will include all or most of the 40 permanent healthcare workers in the newborn care unit who care for patients on bCPAP therapy and have consented to participate in the study.

**Qualitative interviews:** Up to 15 of those same healthcare workers who were observed using the PATH bCPAP kit with blenders will be interviewed within the first five days of their first use of the PATH bCPAP kit with blenders. Additionally, five of those healthcare workers that used the PATH bCPAP and blenders kit three or more times during study period will be interviewed again towards the end of the study to probe if their experience changed with familiarity of use.

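### The raw count of PATH bCPAP infants is a poor input to the integration domain: the enrolment limits largely set it, it tends to rise as blender need falls, and it reflects uptake only when the calendar end binds

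*Combined protocol and SAP*

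**What the plan says.** Section 5.8.2 divides operational feasibility, the first primary objective, into five domains. Each becomes an index with equal weight, and "We will sum these index measures to determine overall operational feasibility". The domain on integration into service delivery has three elements: "Count of patients treated with PATH bCPAP", the frequency of blending by compressor and by PATH blender, and the frequency of known bCPAP complications. Neither 5.8.2 nor Table 13 gives the count a denominator, a target or a scoring direction. Table 13's data sources for this objective are the set-up observation form, Patient Data Form 2 and the concentrator form. The Newborn Unit Shift Form is not among them.

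Section 5.3 (Patients) sets the enrolment limits. "Our aim is to treat 15 patients using the PATH blenders", and "No additional patients will be enrolled in the study after this target has been achieved". Separately, "up to 40 patients will be treated with the PATH bCPAP", a maximum "selected to ensure that we will achieve our required sample size of 15 infants who are treated with the PATH bCPAP kit and blender". What decides blender use is the compressor: "An air compressor will be used as first choice if available". Table 9 adds a calendar end, at 3.5 months of kit use. Table 3 plans on about 12 bCPAP infants a month, a column headed "Enrolled patients with 80% consent", and a compressor being unavailable about half the time.

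**The concern.** A count of treated infants can describe integration only if it moves with how well the kit entered the unit's practice. Here accrual is closed by a quota on a different event, blender use. If most kit infants need a blender, the quota fills early and the count is low. If few do, the count runs on until the cap or the calendar stops it. Two studies in which the kit reached the same share of bCPAP infants could report quite different counts because a compressor worked in one and not in the other.

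At stake is one input to one of five domains of a primary objective. The question the domain should help answer is how far the kit reached the unit's bCPAP infants. Section 5.9.1 says that parents are often absent at initiation and that those infants start on the Kiwoko kit. Without a denominator, the enrolment assumption in Table 3 is also never checked against what happened.

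**Working it through.** **Inputs.** Blender quota 15 and cap 40 (section 5.3); 3.5 months of kit use (Table 9); 80% consent and about 50% blender use (Table 3); bCPAP starts 61/5 = 12.2 per month (Table 3, month 5).

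**Table 3 first.** Month 3: 12.2 × 3 = 36.6 (table 37); 37 × 0.80 = 29.6 (table 29); 29 × 0.50 = 14.5 (table 15). Also 15/0.5 = 30, which matches the 30+ in Figure 9. The plan's own figures reproduce to within rounding.

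**Count under the quota and the cap.** Let p be the share of kit infants who ever use a blender, and N the number enrolled when the 15th is reached, truncated at 40:

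P(N = n) = C(n−1, 14) p^15 (1−p)^(n−15) for n = 15 to 39, with the remainder at 40.

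The mean is close to 15/p until the cap bites. At p = 0.5 the 15th blender infant arrives by infant 40 with probability 0.96.

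**Adding the calendar end.** Let c be the consent share and K the number of consented infants in 3.5 months, taken as Poisson with mean 12.2 × c × 3.5 (34.2 at c = 0.8, 17.1 at c = 0.4). The count is min(N, K), with mean Σ P(N ≥ j) P(K ≥ j) over j = 1 to 40.

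| p | No calendar end | 3.5 months, 80% consent | 3.5 months, 40% consent |
|---|---|---|---|
| 0.8 | 18.7 | 18.7 | about 16 |
| 0.5 | 29.9 | 28.4 | about 17 |
| 0.3 | 39.2 | 33.4 | about 17 |

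At p = 0.5 and 80% consent with the calendar end, enrolment closes on the 15th blender infant in about 72% of cases, on time in about 27% and at the cap in about 1%. Without a calendar end, the mean at p = 0.5 is the same for any consent share; only the duration changes (29.9/12.2 = 2.5 months at 100%, 29.9/4.88 = 6.1 months at 40%).

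**Same count, different reach.** A count near 17 arises with p = 0.9 and 80% consent (15/0.9 = 16.7), and also with p = 0.5 and 40% consent. The kit reached 80% of bCPAP infants in one case and 40% in the other.

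**The share instead.** Kit infants over new bCPAP starts while enrolment was open: 18.75/23.4 at p = 0.8, 30/37.5 at p = 0.5, and 40/50 at p = 0.3 with the cap reached. All equal 80%. Table 3's own month 3 gives 29/37 = 78%. With about 37 starts the standard error is √(0.8 × 0.2/37) = 0.066, so the share is known to about ±13 points (1.96 × 6.6).

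**The case against.** The strongest case against has four parts.

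- **The calendar end matters.** If 3.5 months is a hard stop, the count does respond to uptake (17 against 28.4 at p = 0.5), and at p = 0.3 it averages 33, not close to 40. At 40% consent the relation with blender need nearly vanishes. This stands, and it limits the claim. The documents do not say whether the calendar end overrides an unmet quota.
- **The range of p is assumed.** The only planning value is about 0.5. That figure is the share of time without a compressor, and section 5.5 expects some infants to receive both blending methods, so ever-use may be higher. The low end, p = 0.3, has no support in the text. From p = 0.5 to 0.8 the planned count still moves from 28 to 19.
- **Blending frequency is listed beside the count**, so a careful reader could see what drove it. This helps a narrative report. It does not help an index, because the plan does not say how the elements combine.
- **A share has its own limit.** Sections 5.5 and 5.9.1 keep infants on the Kiwoko kit when research consent is absent, declined or later than 24 hours. The share therefore reflects parental availability and willingness as well as fit with the unit's work. This stands and governs how the share is read; it is still more informative than a count set by a quota.

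**Conclusion.** The raw count is a poor input to the integration domain. Under the planned consent share and a 3.5-month limit its mean runs from about 19 to 28 to 33 as blender use falls from 80% to 50% to 30%, with no change in the share of infants reached. It tracks uptake only when the calendar end binds. These figures assume 12.2 starts a month, Poisson arrivals, and blender need that is independent between infants. Compressor breakdowns affect several infants at once, so the real spread would be wider.

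Three stronger readings are not supported. A reader might infer that the count is wholly fixed by the blender quota and says nothing about uptake; the cap, chance and the calendar end also act, and under the last of these uptake matters. A reader might infer that the plan rewards low blender use; 5.8.2 never says that a larger count scores as better. A reader might also infer that the unit has no record from which to take a denominator; the content of the shift form (Appendix D) is not in the text available, so that cannot be said.

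The point is worth correcting but of moderate weight: it concerns one of three elements in one of five domains of an uncontrolled feasibility study, and no stopping rule or hypothesis test depends on it.

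**What to change.** In 5.8.2 and Table 13:

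- Replace the raw count in the index with PATH kit infants divided by all infants newly started on bCPAP in the unit while enrolment was open.
- Add PATH starts per month (planned value 12.2 × 0.8 = 9.8).
- State which limit closed enrolment: the 15th blender infant, the 40th kit infant or the calendar end.
- Keep the raw count as a descriptive figure only.
- State that the share is reach under the study's consent rule, to be compared with the roughly 80% in Table 3, and is not evidence of routine integration by itself.

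Take the denominator as an aggregate number of new bCPAP starts from unit records or the shift form, and list that source in Table 13. It must count starts, not infants present: shifts last eight hours and median therapy is 3 days, so a census would count the same infant many times. A step-by-step account (parent available, approached, consented) should be added only if the consent log already holds it, because it would otherwise require following infants who were never enrolled.

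The cost is a few changed lines and, if the shift form lacks the item, one added tally per shift.
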